6.3 Statistical Methods

6.3.1 Analysis Plan

Subject demographic and clinical characteristics will be summarized with standard descriptive statistics. Summarized values for the primary and secondary outcomes will be compared between the two treatment arms using paired statistical tests (Wilcoxon signed rank tests, paired t-tests) as appropriate based on the data distribution. Crossover treatment trials traditionally have a washout phase with no treatment in order to determine if all outcome measures are reflective of the current treatment and not remnants of the prior treatment. Ventilation studies are not able to have a washout phase, as it is not possible to stop providing ventilator support for a set timeframe. In addition, the timeframe needed for

a washout is unknown for change in ventilation modes. For the primary analysis, all data will be included in the analysis. As a secondary analysis we will selectively exclude the first 4, 8, and 12 hours of data to determine what washout phase may make a difference in data analysis. This timeframe will be considered a washout out phase to ensure all data collected for each mode of ventilation is related to this mode and not residual effect of the prior mode. Linear mixed effects models will be used to explore longitudinal change in the study outcomes (as continuous measures) as a function of the treatment arm. These models are well suited for repeated measurements in longitudinal studies and are capable of handling unbalanced data if present (e.g. due to drop-out). Random effects terms for both the intercept and slope will be evaluated to account for potential subject specific deviation from the cohort's overall average baseline (intercept) and change over time (slope). Model fit will be assessed using the Akaike Information Criterion.

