Safety Evaluations	Subject safety will be monitored by through assessment of adverse events, vital signs, physical examinations, and laboratory data by the medical and study teams as well as the independent data safety monitoring committee. All study investigators and a core group of respiratory therapists who will care for study infants will be provided training on the Servo I ventilator and the NAVA mode. Clinicians responsible for the care of study subjects receiving the NAVA mode of ventilation will be trained up to the current standard for their role, as is done for clinicians using clinically deployed ventilators. Guidelines for startup and continued management, including troubleshooting techniques of the NAVA mode, will be available for the medical teams and a study investigator will be on call 24/7. Individual subjects will be withdrawn from the study for safety if there is an absolute, sustained increase in FiO ₂ by 20% or if the pCO ₂ /TcO ₂ increase by 25 points above baseline or to a level greater than 90 mm Hg, for more than 2 hours while on the NAVA mode. If this occurs, the patient will discontinue NAVA therapy and be transitioned to previous CMV settings. A study investigator will round daily with the clinical team and be available 24/7 for questions. The overall safety of the study will be assessed with interim safety analyses after the completion of every 5 patients (3 times total) and in the event of any serious safety events.
Statistical and Analytic Plan	Summarized values for the primary and secondary outcomes will be compared between the two treatment arms using paired statistical tests (e.g. Wilcoxon signed rank tests, paired t-tests) as appropriate, based on the data distribution. Linear mixed effects models will be used to explore longitudinal change in the study outcomes (as continuous measures) as a function of the treatment arm.
DATA AND SAFETY MONITORING PLAN	Clinical adverse events will be monitored throughout the study period. There will be monthly and as needed ad-hoc study investigator meetings to discuss and monitor trial data and safety. All data will be kept confidential in accordance with HIPPA and CHOP policies. An independent safety monitoring committee inclusive of physicians from each study site will be formed to review any adverse events, adjudicate relatedness to the study procedures, and recommend trial continuation or early closure.

TABLE 1: SCHEDULE OF STUDY PROCEDURES

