2.1 Primary Objective

To determine whether invasive mechanical ventilation with NAVA, as compared to CMV, improves respiratory gas exchange in prematurely born infants and young children receiving invasive respiratory support for severe BPD.

The primary study outcome is the median, time-weighted daily oxygen saturation index ([mean airway pressure x FiO₂]/SpO₂). Secondary measures of respiratory gas exchange that will be evaluated are the daily median transcutaneous pCO₂ levels (measured hourly) and the daily frequency of intermittent hypoxic events (SpO₂ < 80% for ≥ 10 seconds and less than 3 minutes) recorded by continuous SpO₂ measurement.

We hypothesize that NAVA compared with conventional mechanical ventilation will result in statistically significant reductions (p<0.05) in the median daily oxygen saturation index.

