3 INVESTIGATIONAL PLAN

3.1 General Schema of Study Design

We propose a prospective, randomized cross-over trial comparing NAVA mechanical ventilation to CMV. After a 24-hour observation period to collect baseline Edi data, enrolled preterm infants and young children requiring invasive ventilation for sBPD will undergo two consecutive 5-day treatment periods, one while receiving CMV and the other while receiving NAVA (Figure 1). The treatment order will be determined by randomization. For each study site, the ventilator used for the observation phase and CMV phase of the study will be the standard flow triggered ventilator platform primarily used at each institution for routine clinical care. At CHOP, this is the Dräger V500 ventilator and at Hasboro, this is the Servo U ventilator. Edi will be continuously monitored, recorded, and displayed for all phases of this trial by the servo I or U ventilators, as it has the capability to monitor, record, and display these data while in standby mode.

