3.3.2 Total Number of Study Sites/Total Number of Subjects Projected

The study will be conducted in two intensive care units at CHOP (NI/ICU and PICU) and the PICU at Hasbro Children's Hospital.

Recruitment will stop when 20 subjects successfully complete the trial. It is expected that approximately 25 subjects will be enrolled to produce 20 evaluable subjects.

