6.4 Sample Size and Power

We will enroll up to a total of 25 subjects to generate 20 subjects will have adequate evaluable data, during a proposed 24 month study period. The **Table** shows the number of patients required, with 80% power and $\alpha=0.05$, to detect a range of within subject differences in mean oxygen saturation index (at various within subject standard deviation [SD] levels) between the two treatment periods. As shown, the proposed sample size of 20 subjects will provide sufficient power to detect a range of clinically meaningful differences in oxygen saturation indices with statistical significance.

Table. Minimal detectable difference in mean oxygen saturation index

SD	Detectable difference			
	1	1.5	2	3
0.25	4	3	3	3
0.5	7	5	4	3
1	18	10	7	5
1.5	38	18	11	7
2	65	30	18	10
3	144	65	38	18

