8 STUDY ADMINISTRATION

8.1 Treatment Assignment Methods

8.1.1 Randomization

Computer generated randomization will determine the initial mode of mechanical ventilation. There will be 1 randomization scheme for the entire study (to be used by both sites) to ensure equal allocation of each ventilation mode as the starting mode. Investigators and clinicians will not be blinded to the mode of ventilation as this information is essential for patient management and is easily discovered. However, blinded data analysis will be performed.

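### The primary paired test has no period term although mode order is randomised; the cost is small for small period shifts and grows if the completing sequences are unequal

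*Combined protocol and SAP*

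**What the plan says.** - **Design.** Section 3.1 describes two consecutive 5-day periods, one per mode, and states: "The treatment order will be determined by randomization". Section 8.1.1 uses one scheme for both sites "to ensure equal allocation of each ventilation mode as the starting mode".
- **Primary test.** Under section 6.3.1, summarised values are "compared between the two treatment arms using paired statistical tests (Wilcoxon signed rank tests, paired t-tests) as appropriate based on the data distribution". The synopsis likewise gives "paired statistical tests (e.g. Wilcoxon signed rank tests, paired t-tests) as appropriate, based on the data distribution". Section 2.1 hypothesises "statistically significant reductions (p<0.05) in the median daily oxygen saturation index".
- **Numbers.** Section 3.3.2: "Recruitment will stop when 20 subjects successfully complete the trial", with about 25 enrolled. The section 6.4 table gives the N needed "to detect a range of within subject differences in mean oxygen saturation index" at several within-subject SDs.
- **Neighbouring provisions.** Section 6.3.1 drops the first 4, 8 and 12 hours in secondary analyses, to examine carry-over. It adds: "Linear mixed effects models will be used to explore longitudinal change in the study outcomes". Those models are exploratory and name no period or sequence term.

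**The concern.** A paired test on NAVA-minus-CMV differences pools children who received NAVA second with children who received it first. Any general change between the first and second five days enters with a plus sign in one group and a minus sign in the other.

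With equal groups the change cancels from the mean but stays in the variance, so power is lost. With unequal groups it does not cancel, and part of it is read as a mode effect, in either direction. The plan aims for equal allocation at randomisation, but it stops on total completers rather than completers per order, so the analysed split is not controlled.

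What is at stake is the precision and accuracy of the primary estimate and, at marked imbalance, the 5% error rate. The section 6.4 sample sizes hold for the paired test only if there is no shift.

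**Working it through.** **Inputs from the plan.** n = 20 completers, alpha 0.05 and 80% power (section 6.4; sidedness is not stated, and the table reproduces as two-sided). Worked cell: within-subject SD 1, difference 1.

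**Assumptions.** One summary OSI per child per mode, because section 6.3.1 does not define the summary further. Normal data. A period shift π (period 2 minus period 1) of 0.25, 0.5 or 1 OSI unit. The documents give no value for π. The eligibility criteria exclude recent acute instability, so nothing supports a shift as large as 1; it is shown only as a stress case.

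**Step 1: reproduce the plan's table.** Use a paired t-test with the exact noncentral t and SD of the difference = √2 × within-subject SD. For SD 1 and difference 1 this gives N = 18, as stated. All 24 cells reproduce. The two most extreme cells (SD 0.25, differences 2 and 3) need 3, as stated, because N = 2 gives only 47% and 65% power. At n = 20 with no shift, power is 85.1%.

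**Step 2: effect of a shift on the paired test.** Let δ be the true NAVA-minus-CMV difference, n1 the number completing CMV then NAVA, and n2 the number completing NAVA then CMV. The expected difference is δ + π in the first group and δ − π in the second. Therefore:

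- bias of the mean difference = π(n1 − n2)/n
- expected sample variance = 2·SD² + 4π²·n1·n2/[n(n − 1)]

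At 10:10 and π = 0.5, the bias is 0 and the expected variance is 2 + 4(0.25)(100)/(20 × 19) = 2.26 instead of 2. At 12:8 and π = 0.5, the bias is 0.5 × 4/20 = 0.10.

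**Step 3: period-adjusted analysis.** The estimate is the average of the two group means, with SE = (√2·SD/2)·√(1/n1 + 1/n2) on n − 2 = 18 df. It does not depend on π. At 10:10, SE = 0.7071 × 0.4472 = 0.316, noncentrality 1/0.316 = 3.16 and power 84.8%.

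**Step 4: compare.** Paired t power is given by direction of shift where the split is unequal.

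| Completers | Paired, π = 0.25 | Paired, π = 0.5 | Paired, π = 1 | With period term |
|---|---|---|---|---|
| 10:10 | 84.3% | 81.8% | 71.4% | 84.8% |
| 11:9 | 82–86% | 78–86% | 61–81% | 84.5% |
| 12:8 | 80–88% | 73–89% | 50–88% | 83.4% |

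| Completers | Bias (π = 0.25 / 0.5 / 1) | Paired t type I error (π = 0.25 / 0.5 / 1) |
|---|---|---|
| 10:10 | 0 / 0 / 0 | 4.7 / 3.8 / 1.7% |
| 12:8 | 0.05 / 0.10 / 0.20 | 4.9 / 4.7 / 3.9% |
| 13:7 | 0.075 / 0.15 / 0.30 | 5.3 / 5.9 / 7.3% |

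At 10:10 the period term gains power only for shifts above about 0.13.

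**Step 5: how likely is imbalance?** Assume 25 enrolled as 13:12 and 5 lost at random. The hypergeometric probabilities, with C(25,5) = 53,130, are:

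- 10:10: C(13,3)·C(12,2)/53,130 = 18,876/53,130 = 0.355
- 11:9 either way: 0.484
- 12:8 either way: 0.145
- 13:7: 792/53,130 = 0.015

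Completers are therefore unequal with probability 64%, and 12:8 or worse with probability 16%. Averaged over this loss, paired power is 83.5–84.9% (π = 0.25), 80.0–83.1% (0.5) and 66.8–74.5% (1), against 84.4% adjusted. Mean absolute bias is 0.02 / 0.04 / 0.08, and type I error is 4.8 / 4.1 / 2.4%.

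**Step 6: the rank branch.** At 10:10 the signed-rank test has power 82.5 / 79.8 / 67.7% at the three shifts. The rank-sum test of period differences by order has about 81% at any shift, so it gains only for shifts above about 0.4.

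**The case against.** Under the allocation the plan intends, the paired test is valid: at 10:10 it is unbiased and, if anything, conservative. Type I error passes 5% only at splits such as 13:7, which random loss produces 1.5% of the time. Most of the 64% chance of imbalance is 11:9, where the bias is 0.025 to 0.05 at shifts of 0.25 to 0.5, against a smallest tabulated difference of 1. The shift, the starting split and random loss are all assumed, and the large losses need a shift of 1, which nothing in the documents supports. The mixed models carry a time component, and the study is a pilot.

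All of this stands, and it rules out any claim that the primary analysis is invalid. It does not remove the point. The mixed models are exploratory, name no period term and do not state where time starts, so they may absorb some drift but do not protect the p<0.05 test. Loss need not be random with respect to order. The objection is strongest on the rank branch: with no shift, replacing signed-rank by rank-sum costs about 2 points of power at 10:10 and 5.5 at 13:7, so that change is a genuine trade-off. The t-based change is not open to the same objection.

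**Conclusion.** The concern holds as an improvement the plan should make, not as a fatal flaw. The primary test omits a period term in a randomised-order, two-period design, and nothing else in the plan supplies one for the primary comparison.

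For a balanced trial with shifts up to half the within-subject SD, the harm is at most about 3 points of power. With unequal completing orders the estimate is also biased by π(n1 − n2)/n, and power can move either way. Type I error is a concern only from about 13:7. The missing term is certain from the text. The size of its effect depends on the assumed shift and split, neither of which the documents give.

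**What to change.** - **Primary analysis.** Prespecify the 2×2 crossover analysis of each child's period-level OSI, with mode and period as fixed effects and child as a blocking effect. This is equivalent to a two-sample t-test of period differences between the two orders.
- **Reporting.** Give the number completing each order.
- **Secondary outcomes.** Use the same analysis for those measured in both periods. The two discharge outcomes have one value per child and fall outside it.
- **Mixed models.** Add a fixed period term to the exploratory models.
- **Rank option.** If a rank test is kept for non-normal data, the period-robust choice is the rank-sum test of period differences by order, with its power cost stated.
- **Limit.** State that a period term does not remove carry-over.

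**Cost.** SAP wording, a few lines of code and one degree of freedom (18 rather than 19). With no shift, the t-based analysis loses 0.2 points of power at 10:10, 0.6 at 11:9, 1.7 at 12:8 and 3.7 at 13:7, where power is still 81.4%. Averaged over random loss, the cost is about 0.65 points. N for SD 1 and difference 1 stays 18. Of the 20 table cells with N of 4 or more, 19 are unchanged and one rises from 11 to 12; the four N = 3 cells rise to 4. On the rank branch, the smallest N for 80% power at SD 1 and difference 1 rises from 19 to 20, which leaves no spare completers.

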3.1.2 Study Observation Phase

Prior to beginning the initial treatment phase, all subjects will undergo a 24-hour period of observation with an Edi catheter in place while receiving CMV as ordered by the primary medical team. This period will be used to establish baseline Edi (Edi peak and Edi min), positive inspiratory pressure (PIP), and transcutaneous pCO₂ levels that will be employed in the study treatment phase.

At the end of the 11-day treatment phase, a second observation phase will begin and will be limited to medical record review. This phase will continue until the child is discharged in order to ascertain age and respiratory support needs at discharge.

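### The washout check in Section 6.3.1 stops at 12 of 120 hours, so similar results across its windows could falsely reassure if lag between modes lasts about a day or more

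*Combined protocol and SAP*

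**What the plan says.** Section 3.1 describes "two consecutive 5-day treatment periods, one while receiving CMV and the other while receiving NAVA". There is no gap between the periods, and Section 6.3.1 explains why: ventilator support cannot be suspended. The same section adds that the timeframe needed for "a washout is unknown for change in ventilation modes".

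The analysis then has two layers. The primary layer removes nothing: "For the primary analysis, all data will be included in the analysis". The secondary layer is the washout check: "As a secondary analysis we will selectively exclude the first 4, 8, and 12 hours of data", with the purpose "to determine what washout phase may make a difference in data analysis". I read this as applying to each mode's period, since the section goes on to speak of the data collected for each mode. No longer window is listed, and no criterion is given for what counts as a difference.

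Before randomization, "all subjects will undergo a 24-hour period of observation with an Edi catheter in place while receiving CMV" (Section 3.1.2).

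Section 2.1 defines the primary outcome with a median: "The primary study outcome is the median, time-weighted daily oxygen saturation index". Section 6.1 calls it a mean. Section 6.3.1 compares summarized values by paired t-test or Wilcoxon signed rank test. It also plans exploratory linear mixed models of longitudinal change by treatment arm. No period, sequence or carry-over term is stated.

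**The concern.** A search for an unknown duration cannot find one beyond its own upper limit. Here the limit is 12 hours, while many outcomes are daily summaries over five days: OSI, sedation dose, comfort scores, asynchrony index and cortisol. Some of these depend on clinicians adjusting support and sedation, so lag longer than 12 hours is possible, though the documents give no figure for it.

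Lag does not cancel in this design. The observation day is on CMV, so every NAVA period follows CMV. CMV given first also follows CMV, and only CMV given second follows NAVA. Slow onset of a NAVA effect and its persistence into CMV both pull the NAVA-CMV difference toward zero.

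The stake is how the pilot is read. If the 0, 4, 8 and 12 hour results look alike, a reader may take the effect size as free of lag and carry it into the planning of a later trial.

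**Working it through.** **Inputs from the documents.** Period length: 5 days = 120 h (Section 3.1). Windows: 4, 8 and 12 h (Section 6.3.1), which are 3.3%, 6.7% and 10% of a period. State before period 1: CMV (Section 3.1.2). Evaluable subjects: 20 (Section 6.4).

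**Assumptions.** The NAVA effect builds up and wears off exponentially with a common half-life; the two sequences are equal in size; the true effect is 1. The half-life is not in the documents, so a range is shown.

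**The plan's own figure.** The Section 6.4 table reproduces as a two-sided paired t-test with SD of the difference = √2 × the tabled SD. For example, SD 1 and difference 1 give 18, as stated; 22 of 24 cells match exactly and the other two differ by 1. The table is not in dispute. It supplies the standard error used below.

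**Formulas.** Let λ = ln 2 / half-life. The mean residual over hours a to 120 of a period is

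r(a) = (e^(−λa) − e^(−120λ)) / (λ(120 − a)).

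- CMV first: difference = 1 − r. CMV follows CMV, so only NAVA onset is delayed.
- NAVA first: difference = (1 − r) − (1 − e^(−120λ)) r. Onset is delayed, and the NAVA effect reached by hour 120 decays through the CMV period.
- The estimate is the average of the two.

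**24-hour half-life.** λ = 0.02888 and e^(−120λ) = 0.03125.

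- All data: r = 0.96875 / (0.02888 × 120) = 0.2795. CMV first gives 0.72, NAVA first 0.45, average 0.585.
- After 12 h: r = (0.7071 − 0.03125) / (0.02888 × 108) = 0.2167, average 0.678.
- After 24 h: r = (0.5 − 0.03125) / (0.02888 × 96) = 0.1691, average 0.749.
- After 48 h: r = (0.25 − 0.03125) / (0.02888 × 72) = 0.1052, average 0.844.

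Dropping 12 h removes 1 − 0.2167/0.2795 = 22% of the dilution; dropping 48 h removes 1 − 0.1052/0.2795 = 62%.

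**Estimate from period means, true effect 1:**

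| Half-life | All data | Drop 12 h | Drop 24 h | Drop 48 h |
|---|---|---|---|---|
| 4 h | 0.93 | 0.99 | 1.00 | 1.00 |
| 12 h | 0.78 | 0.88 | 0.93 | 0.98 |
| 24 h | 0.59 | 0.68 | 0.75 | 0.84 |
| 48 h | 0.33 | 0.40 | 0.46 | 0.56 |

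**Visibility.** At a 24-hour half-life the 0 to 12 h shift is 0.678 − 0.585 = 0.09. With 20 subjects and within-subject SD 1, the standard error of the mode difference is √2 × 1/√20 = 0.32. Four estimates set side by side would look much alike.

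**Median of five daily values.** With steady build-up or decay the median is the day-3 value. Windows up to 12 h touch only day 1, which is already the extreme value. At a 24-hour half-life the estimate is 0.74 at 0, 4, 8 and 12 h, then 0.80 after 24 h and 0.87 after 48 h. In simulations with assumed hourly noise (20 subjects, 600 runs), 21% to 34% of period medians did change, and the mode difference moved by about 0.03 to 0.06 OSI per 1 OSI of true effect.

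**The case against.** Several points on the other side stand.

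- Long lag is not shown. Section 1.2 says NAVA pressure is set breath by breath, and the studies described in Section 1.3.1.2 report synchrony effects in comparisons as short as 10 minutes. If lag is short, the present windows do their job: 72% of the dilution is removed at a 6-hour half-life and 98% at 2 hours. But one 10-minute study in the same section found no oxygenation difference, and sedation or cortisol may respond more slowly.
- On the mean, the estimate at a 24-hour half-life rises steadily (0.59, 0.62, 0.65, 0.68), which is itself a sign of lag. In the simulations a formal paired test of the 12-hour shift detected it in 73% to 90% of runs at half-lives of 6 to 48 hours for the mean, but in only 9% to 23% for the median. The plan specifies no such test.
- The mixed models in Section 6.3.1 could show drift within a period by mode, although they are exploratory and no carry-over, period or sequence term is stated.
- Not all of the dilution is carry-over. At a 24-hour half-life, 0.28 of the 0.415 is slow onset of NAVA and 0.135 is NAVA persisting into CMV. Slow onset is arguably part of a 5-day comparison.

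A reader might infer that the check cannot detect carry-over at all, or that the trial will wrongly report that no washout is needed. The documents support neither. The first needs a noise-free median taken across daily values, while Section 6.1 says mean and Section 2.1 can also mean a median within each day. The second needs day-scale lag, which is not established, and a decision rule that the plan does not contain.

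**Conclusion.** The concern holds conditionally. The windows suit lag of a few hours and are too short to characterize lag of about a day or more. At an assumed 24-hour half-life, 78% of the dilution in the period mean is still present after the longest planned exclusion (0.2167/0.2795). At 4 hours or less, the 12-hour window brings the estimate to at least 0.99 of the true effect. Because the plan says the duration is unknown, similar estimates from 0 to 12 hours cannot be read as absence of lag, least of all if the period summary is a median of daily values.

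These sizes rest on exponential build-up and decay, equal sequences and assumed half-lives. They show what the check can and cannot resolve; they do not predict the bias in this trial. The all-data primary analysis is not in question here.

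**What to change.** Keep the all-data primary analysis and the 4, 8 and 12 hour windows. In Section 6.3.1:

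1. Add exclusions of the first 24 and 48 hours of each period. Whole days keep daily counts, doses and averages intact. A 72-hour exclusion is optional, since only two days per mode would remain.
2. Report the NAVA-CMV difference with its confidence interval for every window, overall and by sequence, because what precedes CMV differs between the sequences.
3. State that similar estimates at 4 to 12 hours do not rule out longer lag.

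I would not add a rule that the estimate must be stable across windows. With 20 subjects, 0.84 after 48 hours and 0.90 after 72 hours (24-hour half-life) could pass as stable while still diluted.

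The cost is a few lines of text and extra runs on data already collected. The later windows use three or four days per mode (two at 72 hours), so their intervals will be wider, and more so by sequence.
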